## Power analysis

Power analyses are based on effect sizes from mindfulness-based interventions for individuals with depression and anxiety reflecting (1) pre-post changes in depression and anxiety and (2) association between practice dosage and changes in psychological symptoms. For pre-post changes in depression and anxiety, Goldberg et al. (2018) conducted a meta-analysis of mindfulness-based interventions (MBIs) versus no treatment control conditions in individuals with depression or anxiety and found mean between-group effects in the moderate to large range (ds = 0.59 and 0.89, for depression and anxiety, respectively). To our knowledge, no meta-analysis has been conducted evaluating pre-post changes in depression and anxiety within clinical samples using mobile health MBIs. Moderate to large reductions in depression symptoms have been reported in several mobile health MBI studies with depressed samples (d = 1.09 in Dimidjian et al., 2014, ds = 1.15 to 1.21 in Ly et al., 2014) and large reductions in anxiety have also been reported in anxious samples (d = 1.33; Boettcher et al., 2014).

For the association between practice dosage and changes in psychological symptoms, Parsons et al. (2017) conducted a meta-analysis showing a small magnitude correlation (r = .26). Data from a pilot study using the HMP app in a very small sample (n = 10) also showed moderate-to-large reductions in *DASS-21* stress (d = 0.78) and a correlation between practice time and pre-post changes in stress (r = .27); however, small studies provide a poor basis for conducting power analysis (Leon et al., 2011).

Power for between-group differences in dosage based on randomization to dosage conditions can be roughly estimated based on our preliminary feasibility data (n = 85). Participants will be randomized to 15- and 5-minute dosages. Our naturalistic pilot data showed a mean practice time of 3.91 minutes per day (SD = 3.15, range = 0.0 to 12.2). Assuming randomization produces a 3-minute mean difference between groups (e.g., means of 7 and 4 minutes per day, for 15- and 5-minute dosage conditions) and doubles the standard deviation, there would be a between-group effect of d = 0.48.

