Healthy Minds Program (HMP) App Dosage Study

Basic Study Information

[name]

NCT05229406

Minimal Risk Research Institutional Review Board

IRB Approval Date: 10/19/2022

[compiled from the non-protocol based IRB application]

Healthy Minds Program App Dosage Study

Principal Investigator: [name]

Funding: Mindfulness training delivered via mobile health to reduce depression and anxiety

1K23AT010879-01

Overall Purpose

This study will investigate the impact of dosage of meditation practice delivered via a mobile health smartphone application (Healthy Minds Program app) on symptoms of depression and anxiety. We will also investigate the feasibility and acceptability of this program among individuals with elevated symptoms of depression and/or anxiety at baseline.

Study Procedures and Interventions

We anticipate enrolling 110 participants into the study. Recruitment will take place via email, newspaper advertisements, Craigslist, clinics, and flyers. Interested individuals will complete a webscreen to determine eligibility. After passing the webscreen, they will be provided with an overview of the study and will have the option to enroll via an online consent process.

Participants will be asked to complete T1 surveys. After completing T1 surveys, they will be contacted by study staff and assigned to a dosage condition (low dosage = 5 minutes per day, high dosage = 15 minutes per day). Study staff will assist with downloading the mobile app, briefly introducing the participant to the meditation practices, and answering any questions about the practices and/or study. Participants will complete EMA assessments (brief questionnaires delivered as text messages to participants' mobile phones) throughout the duration of the study. Four EMA questionnaires will be delivered per day at random times interspersed between the hours of 9am and 7pm. Participants will complete T2 surveys approximately 4 weeks

after T1. Participants may be invited to an exit interview after completion of the study in order to give feedback on the study.

- Attitudes Towards Psychological Online Interventions (T1, T2)
- AUDIT C (screening only)
- Big Five Inventory, Conscientiousness Items (T1 only)
- Demographics (T1 only)
- Digital Working Alliance Inventory (T2 only)
- EMA items (daily throughout study)
- Experiences Questionnaire decentering subscale (T1, T2)
- Five Facet Mindfulness Questionnaire awareness subscale (T1, T2)
- Healthy Minds Index (T1, T2)

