## **Analysis approach**

The feasibility and acceptability of the HMP app for individuals with depression and anxiety will be assessed using benchmarks previously recommended for mHealth research (Hermes et al., 2019). The app will be considered acceptable if ≥75% of participants complete the intervention and adhere to treatment for an average of 7- or 3-minutes per day (for the 15- and 5-minute dosage conditions), 6 days per week. A usability score > 70 on the Systems Usability Scale (Bangor et al., 2008) will be considered acceptable. As our study is not designed nor powered for definitive effectiveness analyses, Cohen's (1988) d effect sizes will be used to estimate the magnitude of pre-post changes in symptoms of depression and anxiety. The effect of group assignment on practice dosage will be analyzed using analysis of variance (ANOVA) covarying gender. The relationship between practice dosage and changes in depression and anxiety will be assessed using ordinary least squares regression (OLS) models predicting post-treatment symptom levels while controlling for pre-treatment symptoms and gender. Intensive longitudinal data (i.e., ecological momentary assessment data) will be analyzed using dynamic structural equation modeling (DSEM), accounting for the nesting of observations longitudinally within participants. Cross-lagged models will be constructed to evaluate the temporal sequencing between practice time with mood symptoms (depression, anxiety) and candidate mechanisms (decentering, repetitive negative thinking). DSEM will allow both practice dosage and outcomes (symptoms, mechanisms) to be modeled simultaneously (Hamaker et al., 2018). DSEM also allows assessment of between-person variability in cross-lagged relationships that can inform power analysis for future studies as well as provide substantively useful information regarding individual differences in the link between practice dosage, symptoms, and mechanisms.

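### The planning effect d = 0.48 puts one doubled SD of 6.3 min/day on both arms, which is implausible though conservative for the 5-minute arm; between-group power at 81 completers should be a range of about 56% to 81%, not 85%

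*SAP*

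**What the plan says.** The Protocol (Study Procedures and Interventions) defines the two arms as "low dosage = 5 minutes per day, high dosage = 15 minutes per day". The SAP (Power analysis) says that power for the difference in practice time between them "can be roughly estimated based on our preliminary feasibility data (n = 85" in number). Its inputs are these:

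- Pilot: "Our naturalistic pilot data showed a mean practice time of 3.91 minutes per day (SD = 3.15, range = 0.0 to 12.2").
- Difference: "Assuming randomization produces a 3-minute mean difference between groups", illustrated by "e.g., means of 7 and 4 minutes per day, for 15- and 5-minute dosage conditions".
- Spread and result: "and doubles the standard deviation, there would be a between-group effect of d = 0.48".

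No SD is given by arm, so a single value of 2 × 3.15 = 6.3 min/day applies to both. Later in the same section the SAP plans 90 participants, expects 81 with complete data, and states 85% power for the between-group difference on the basis of this effect size (which it there labels r = .26). It concludes that the sample is large enough for this comparison.

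On the analysis, the SAP (Analysis approach) states: "The effect of group assignment on practice dosage will be analyzed using analysis of variance (ANOVA) covarying gender". It does not say how unequal variances would be handled.

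**The concern.** The doubled SD sits badly with the 5-minute arm. Practice minutes cannot be negative, and the assumed mean of 4 is almost the pilot mean of 3.91, where the observed SD was 3.15. The SAP does not say why an instruction to practise 5 minutes a day should leave the mean where it was and double the spread. A wider spread is easier to accept in the 15-minute arm.

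This matters because d = 0.48 is the only planning effect the SAP derives for a randomised comparison, and the claim of adequate power is built on it. The 85% figure also has a problem of its own, shown below. If only that is repaired and the common SD is kept, the SAP would report 56% from a spread that its own pilot data make doubtful. The study is meant to inform later trials, so the assumed SD of practice time should be one that a reader can follow.

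A secondary point is that arms asked for 5 and 15 minutes can be expected to differ in spread, whereas a standard ANOVA assumes they do not.

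**Working it through.** **Inputs from the SAP.** Pilot mean 3.91, SD 3.15, range 0.0 to 12.2 min/day; arm means 4 and 7; SD doubled; 81 completers in total; stated power 85%.

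**Assumptions, because the documents are silent.** Two-sided 5% test; 1:1 allocation (40 and 41 completers); gender covariate ignored.

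**1. The SAP's effect size.** d = 3/(2 × 3.15) = 3/6.3 = 0.476, which rounds to 0.48. It reproduces.

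**2. What SD 6.3 requires.** A variable between 0 and b with mean m has SD of at most √[m(b − m)]. Turned round, SD s needs b ≥ m + s²/m, with s² = 39.69.

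- 5-minute arm, m = 4: b ≥ 4 + 39.69/4 = 13.9 min/day.
- 15-minute arm, m = 7: b ≥ 7 + 39.69/7 = 12.7 min/day.
- Largest SD at mean 4 within the pilot range: √(4 × 8.2) = 5.73, reached only if everyone averages 0 or 12.2.
- Largest SD at mean 4 if nobody exceeds 5 minutes: √(4 × 1) = 2.0.
- Coefficients of variation: pilot 3.15/3.91 = 0.81; 5-minute arm 6.3/4 = 1.58; 15-minute arm 6.3/7 = 0.90.

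The result does not hang on the example mean of 4. Within 0 to 12.2 no mean allows an SD above 12.2/2 = 6.1.

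SD 6.3 is therefore close to the pilot's relative spread in the 15-minute arm, and about twice that spread in the 5-minute arm.

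**3. Power under arm-specific SDs.** Pooled SD = √[(s₁² + s₂²)/2]; d = 3/pooled SD; noncentrality = d × √(40 × 41/81) = d × 4.50; 79 degrees of freedom, critical t = 1.99.

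| SD, 5-min arm | SD, 15-min arm | Pooled SD | d | Noncentrality | Power, 81 in total |
|---|---|---|---|---|---|
| 6.3 (as written) | 6.3 | 6.30 | 0.48 | 2.14 | 56% |
| 3.15 (pilot) | 6.3 | 4.98 | 0.60 | 2.71 | 76% |
| 2.0 (nobody above 5 min) | 6.3 | 4.67 | 0.64 | 2.89 | 81% |

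Two further cases show the direction. Keeping the pilot coefficient of variation in both arms (SDs 3.22 and 5.64) gives d = 0.65 and 83%. Not doubling at all gives d = 3/3.15 = 0.95 and 99%.

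**4. The stated 85%.** With d = 0.476 and 81 per arm, noncentrality is 0.476 × √(81/2) = 3.03 and power is 85%. With 81 in total it is 56% two-sided (68% one-sided). The total appears to have been entered as the number per arm.

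**5. The ANOVA under unequal spread.** Simulated normal data with no true difference, SD 6.3 in the 15-minute arm, 200,000 trials per row, nominal 5%:

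| Completers, 5-min / 15-min arm | Pooled test, 5-min SD 3.15 | Pooled test, 5-min SD 2.0 |
|---|---|---|
| 40 / 41 | 5.0% | 5.0% |
| 43 / 38 | 6.1% | 6.4% |
| 45 / 36 | 6.8% | 7.6% |
| 38 / 43 | 4.2% | 4.1% |
| 36 / 45 | 3.7% | 3.3% |

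The Welch test stayed between 4.9% and 5.1% in every row.

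**The case against.** The case for leaving the text alone has four parts.

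**There is no calculation error in d.** This stands. A reader might infer that the effect size is wrong; it follows exactly from its inputs, and the weakness lies in one assumption.

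**SD 6.3 at mean 4 is possible.** This also stands. A reader might infer that the input is self-contradictory. But neither document caps recorded practice at the assigned minutes, the app logs actual listening, and 12.2 is the highest value seen among 85 pilot users, not a limit. A skewed gamma distribution with mean 4 and SD 6.3 exists; it would put about 6% of the 5-minute arm above 15 min/day. That is hard to believe, but it cannot be excluded.

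**The assumption is cautious and openly rough.** The SAP calls the estimate rough and gives the means as an example. Doubling lowers d from 0.95 to 0.48, and more plausible SDs raise power. So the SD assumption does not flatter the study. A reader might go further and say that plausible SDs bring power near 85% anyway. The documents do not support that defence: the SAP bases the 85% on the effect size it derived, and that effect with 81 in total gives 56%.

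**The ANOVA is sound as planned.** A reader might infer that the analysis rests on the planning SD, or is invalid. It does not: the model estimates variance from the trial data, and with near-equal arms its error rate is 5%. No passage predicts unequal arms in either direction, and the actual SDs are unknown. What remains is that neither the allocation ratio nor any protection against imbalance is stated, so a robust standard error is a reasonable precaution.

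**Conclusion.** The point holds as one about an unexplained planning assumption and the power figure attached to it. A common SD of 6.3 is implausible for the 5-minute arm and should be justified or replaced by arm-specific values. It does not inflate d.

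With 81 completers in total, power for the difference in practice time runs from 56% to 81% across the three SD pairs in the first table. The claim of 85% does not follow from d = 0.48. These figures assume a two-sided 5% test, equal allocation and the 3-minute difference. The 3.15 and 2.0 for the 5-minute arm are illustrations, so d = 0.60 should not simply replace 0.48 as the one planning value.

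On the analysis, the effect is conditional. If spreads differ as assumed, the pooled test's type I error is about 6% to 7.5% when the 5-minute arm is the larger, roughly 3.3% to 4.2% when it is the smaller, and 5% at 40/41.

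**What to change.** In the SAP, Power analysis:

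- State an SD for each arm with a reason, and state alpha, sidedness and allocation ratio.
- Replace the 85% by power at 81 completers in total, given as a range: 56% (SDs 6.3 and 6.3, d = 0.48), 76% (3.15 and 6.3, d = 0.60) and 81% (2.0 and 6.3, d = 0.64).
- Align the r = .26 label with the effect used: d = 0.476 corresponds to r = 0.476/√(0.476² + 4) = 0.23.
- Reword the conclusion that the sample is sufficient for this comparison to match the range.

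In the SAP, Analysis approach, specify an HC3 standard error for the arm effect in the gender-adjusted model of practice minutes, or a Welch-type equivalent.

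The cost is a few sentences of text and one software option. No additional participants or data are needed.
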